**Analysis Plan**

the closest previous non-missing value. Note that if a subject has missing values immediately after baseline, the baseline observation will not be carried forward and these values will be left as missing, with the exception of the primary efficacy variable of CS dose, for which the baseline value is eligible for the WOCF algorithm only.

For the same efficacy endpoints above that utilize the LOCF/WOCF algorithm, separate analyses will also be performed using observed data only without imputing any missing data. This non-imputation method will be referred to as the OC.

Missing values for the binary endpoints (e.g., whether or not the subject experienced CS dose reduction) will be handled similarly as for the continuous endpoints. First, the LOCF/WOCF algorithm above will be used to impute the (continuous) missing values. The imputed values will then be used to derive the binary endpoints. The binary endpoints will also be analyzed with the OC approach.

Efficacy analyses will be performed on the mITT population using both the LOCF/WOCF and OC approaches with regards to the missing data, which should allow for more robust assessments of efficacy. See Section 16 for the set of analyses using each of the two approaches. The LOCF/WOCF endpoint row in by-visit listings will indicate the value that was used in the LOCF/WOCF efficacy analysis.

The total scores of QMG, MG Composite, MG-QOL 15, MG-ADL and World Health Organization – Five Well Being Index (WHO-5; see Section 16.3.1.14) are calculated and reported in the eCRF. If one or more items are missing at a given assessment, the total score will be set to missing.

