Appendix 3 QMG Score Test Items

Subjects receiving cholinesterase inhibitors will be instructed not to take medication 12 hours prior to assessments such as QMG Score. Scores for each individual item are added together for total score (range 0-39).

TEST ITEMS WEAKNESS	NONE	MILD	MODERATE	SEVERE	SCORE
GRADE	0	1	2	3	6
Double vision (lateral gaze) Sec.	60	11-59	1-10	Spontaneous	
Ptosis (upward gaze) Sec.	60	11-59	1-10	Spontaneous	č.
Facial Muscles	Normal lid closure	Complete, weak, some resistance	Complete, without resistance	Incomplete	20
Swallowing 4 oz. Water (1/2 cup)	Normal	Minimal coughing or throat clearing	Severe coughing Choking or nasal regurgitation	Cannot swallow (test not attempted)	
Speech following counting aloud from 1-50 (onset of dysarthria)	None at #50	Dysarthria at #30-49	Dysarthria at #10-29	Dysarthria at #9	2
Right arm outstretched (90°, sitting) Sec.	240	90-239	10-89	0-9	
Left arm outstretched (90°, sitting) Sec.	240	90-239	10-89	0-9	
Forced vital capacity	> 80%	65-79%	50-64%	<50%	
Rt hand grip: male (Kg) : female	≥45 ≥30	15-44 10-29	5-14 5-9	0-4 0-4	
Left hand grip: male (Kg) : female	≥35 ≥25	15-34 10-24	5-14 5-9	0-4 0-4	
Head, lifted (45%, supine) Sec.	120	30-119	1-29	0	
Right leg outstretched (45-50%,supine) Sec.	100	31-99	1-30	0	2
Left leg outstretched (45-50%, supine) Sec.	100	31-99	1-30	0	

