## 16.2. SECONDARY EFFICACY

### 16.2.1. SECONDARY EFFICACY VARIABLES & DERIVATIONS

#### 16.2.1.1. Percent Reduction in Daily CS (Prednisone or Equivalent) Dose from Baseline to Week 39

Percent reduction in daily CS (prednisone or equivalent) dose is defined in Section 16.1.1.

#### 16.2.1.2. Time to First Episode of MG Worsening from Baseline through Week 39

MG worsening is defined in Section 3.3.3 of the protocol as at least a 4-point increase in QMG total score from Baseline. Time to first episode of MG worsening from baseline through Week 39 is calculated as the date of the first QMG assessment meeting the MG worsening criterion – date of baseline visit + 1. Subjects who never experience MG worsening through Week 39 will be censored at the date of their last non-missing QMG total score assessment on or prior to the date of visit for Week 39.

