**16.3.1.11. CFB in QMG at Week 39, Week 42 and Week 45**

The QMG consists of 13 individual items. The results of the QMG items are entered on the eCRF. The QMG is shown in Appendix 3.

The QMG total score is the sum of all 13 items (scored individually from 0-3) and ranges from 0 to 39. Higher item values represent greater severity of illness. If one or more individual items are missing, the QMG total score will be set to missing. Note that total scores are reported on the eCRF and in general will not be recalculated.

The CFB is calculated as indicated in section 6.7.

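### A QMG with any item missing is discarded even when the recorded items already prove MG worsening, so a first event can be delayed or lost; the expected effect is small

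*SAP*

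**What the plan says.** SAP 7.3 applies one rule to five scales, including the QMG: "If one or more items are missing at a given assessment, the total score will be set to missing". SAP 16.3.1.11 repeats it for this scale: "If one or more individual items are missing, the QMG total score will be set to missing". The same section gives the structure of the score, "The QMG total score is the sum of all 13 items (scored individually from 0-3) and ranges from 0 to 39", and adds: "Note that total scores are reported on the eCRF and in general will not be recalculated".

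The secondary endpoint in SAP 16.2.1.2 rests on that total. MG worsening is defined "as at least a 4-point increase in QMG total score from Baseline". Time to the first episode is "calculated as the date of the first QMG assessment meeting the MG worsening criterion", counted from the baseline visit. A subject with no event is "censored at the date of their last non-missing QMG total score assessment" on or before the Week 39 visit. SAP 16.2.2.2 recognises an event only from the assessments that are available.

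The exploratory endpoint in SAP 16.3.1.8 counts the QMG assessments at which the total is at least 4 above Baseline. SAP 16.3.2.1 rules out imputation for it.

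**The concern.** No QMG item can be negative, so the sum of the recorded items can never exceed the true total. When that sum is already 4 or more above the Baseline total, the definition of worsening is met whatever the blank item would have scored. The SAP still voids the total, and the assessment can then be neither an event nor follow-up.

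The loss can be permanent. In the taper phase, worsening leads to a corticosteroid (CS) increase (Protocol 3.3.3). A subject who stays in the study is expected to return to within 3 points of Baseline (Protocol 3.1 and 3.3.4), which is below the event threshold. If the site acts on a partly scored QMG and the subject responds, the next complete QMG may show no event, and the subject is analysed as never having worsened. A subject who withdraws may have the incomplete QMG as the last one, and is then censored just before a proven event.

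**Working it through.** **Design figure.** The plan gives no event rate or power for time to worsening. Its only sample-size figure is for the primary endpoint: 24 per arm for 70% versus 30%, and 60 after 20% discontinuation. It reproduces (pooled variance, no continuity correction, two-sided 0.05: 24 per arm, power 81.2%; 48/0.8 = 60) and does not depend on the QMG.

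**1. What the recorded items prove.** Let B be the Baseline total, S the sum of recorded items and m the number missing. With items scored 0-3 (SAP 16.3.1.11), the true total lies between S and S + 3m.
- Worsening is proven if S ≥ B + 4.
- No worsening is proven if S + 3m < B + 4.
- Otherwise the assessment is undetermined.

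Example with B = 10 and m = 1: S = 16 means a true rise of 6 to 9, a certain event. S = 10 means a total of at most 13, a certain non-event. S = 11, 12 or 13 is undetermined.

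**2. Which true rises can be proven.** With one item missing, a true rise r is provable if the missing item's true score is at most r − 4.

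| True rise | Provable if the missing item would score |
|---|---|
| 4 | 0 |
| 5 | 0-1 |
| 6 | 0-2 |
| 7 or more | anything |

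With two items missing, proof is guaranteed from a rise of 4 + 6 = 10.

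**3. Does another rule recover the event?** SAP 7.3 fills intermittent gaps in efficacy variables with the previous value. If that applied here, the value before a first event would be below the threshold. SAP 16.2.2.2 needs an available assessment, and a voided total is not one. SAP 16.3.2.1 bars imputation for the episode count. Nothing recovers it.

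**4. Share provable (simulation, assumed inputs).** Thirteen independent items, mean Baseline total 6, 10 or 14, mean rise 2, 4 or 6, and one item missing at random. Among true rises of 4 or more, 34% to 85% are provable from the other 12 items.

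**5. First events affected (assumed inputs).** With 30 per arm and worsening in 60% versus 30%, first events = 30 × (0.6 + 0.3) = 27. Multiply by the share of assessments with a missing item and by the provable share, taking missingness as unrelated to worsening:
- 1% to 3%: from 27 × 0.01 × 0.34 = 0.09 to 27 × 0.03 × 0.85 = 0.69
- 5%: 27 × 0.05 × 0.34 = 0.46 to 27 × 0.05 × 0.85 = 1.15
- 10%: 27 × 0.10 × 0.34 = 0.92 to 27 × 0.10 × 0.85 = 2.30

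**6. Delayed or lost.** If a share p of assessments is incomplete and the rise persists to one later visit with probability q, the share of first events never counted is p × [1 − q(1 − p)], provable or not.

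| p | q = 1 | q = 0.5 | q = 0 |
|---|---|---|---|
| 1% | 0.01% | 0.5% | 1% |
| 5% | 0.25% | 2.6% | 5% |
| 10% | 1% | 5.5% | 10% |

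**7. Power (same assumed rates).** Hazard ratio = ln(0.7)/ln(0.4) = 0.389. Log-rank power by the Schoenfeld formula is 68.8% with 27 events, 68.4% after losing 1% of them, 66.6% after 5% and 64.3% after 10%. These overstate what a fix could recover, because they treat every affected event as lost and provable.

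**The case against.** The case against giving this weight is strong, and most of it stands.

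- **Size.** A reader might take all incomplete assessments as lost events: 13 post-baseline visits × 60 subjects = 780, of which 1-3% is 8 to 23. That counts discarded totals at an assumed rate. A lost first event must also be a first worsening, be provable, and not be picked up later. The 780 is itself a ceiling, because it ignores discontinuation.
- **Differential loss.** A reader might infer that weak subjects leave effort items blank, so that events vanish mainly in the sicker arm. The documents do not support this. The QMG form scores inability as 3: arm hold 0-9 s, leg hold or head lift 0 s, grip 0-4 kg, vital capacity below 50%, and swallowing not attempted. Only swallowing has an explicit not-attempted category, so blanks elsewhere remain possible, but nothing shows that they differ by arm.
- **Dropped events.** QMG is scheduled every 3 weeks, and unscheduled assessments also count. A persistent rise is recorded late, not dropped.
- **A one-sided fix.** Counting only proven events looks free of cost, but it is not. Incomplete visits would then enter the analysis only as events, while visits that prove no worsening would add no follow-up, which pushes the event probability upward.
- **Stakes.** SAP 7.4 calls this a Phase 2 proof-of-concept study with nominal p-values for secondary endpoints, and the episode count is exploratory.

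What survives is the logical gap: the rule as written classes some certain events as missing.

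**Conclusion.** The point holds in a narrow form. With one item missing, any true rise of 7 or more is proven by the other 12 items, yet the SAP does not count it at that visit. Rises of 4 to 6 are provable only when the missing item would score low enough. The first event is delayed if the rise lasts to the next complete QMG, and lost if it resolves first or no complete QMG follows. The episode count is one too low in either case.

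The size cannot be fixed from the documents, which give no missing-item rate. On the assumptions above, the expected effect is below one first event at 1-3% missing, and about 0.9 to 2.3 at 10%. It would be larger if blanks cluster at worsening visits, which the documents neither show nor exclude. The primary CS-dose endpoint does not use the QMG total and is unaffected. Severity is minor.

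**What to change.** Add a rule to SAP 16.2.1.2 and 16.3.1.8, cross-referenced from 7.3, for the worsening endpoints only. When one or more QMG items are missing at a post-baseline assessment:

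1. Classify it as MG worsening if the sum of recorded items is at least the Baseline total + 4.
2. Classify it as a non-event that extends follow-up if the sum of recorded items + 3 × the number of missing items is less than the Baseline total + 4.
3. Otherwise leave it missing.

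Keep the total missing for all change-from-baseline analyses. State also whether the carry-forward rule in 7.3 applies to time to worsening.

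The cost is a few lines of SAP text and code, with no new data, because item scores are already on the eCRF. The downside is small: these two endpoints would use a derivation from items, departing from the uniform scoring rule and from the general policy of not recalculating totals. The rule should be fixed before unblinding.

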## 7.4. MULTIPLE COMPARISONS/ MULTIPLICITY

There will be no adjustment for multiple comparisons/multiplicity in this Phase 2 proof of concept study. All secondary and exploratory endpoints will be evaluated statistically and will have the corresponding results presented with 95% confidence intervals and nominal p-values.

## 7.5. EXAMINATION OF SUBGROUPS

Subgroup analyses will be conducted as stated in the exploratory analysis sections. It should be noted that the study was not designed to detect treatment differences with high statistical power within subgroups.

The following subgroups will be assessed and described within the exploratory analysis sections:

- Stratification categories in terms of Baseline CS dose level at the time of randomization:
  - o 15 mg – 40 mg per day
  - o 41 mg – 60 mg per day
- Baseline QMG categories in relation to the median Baseline QMG across all subjects:
  - o < median
  - o ≥ median
- Sex:

Document: CCI

Author: PPD

Version Number:

Version Date:

Final 2.0  
12Apr2019

Template No: CCI

Effective Date: 01Apr2016

Reference: CCI

Copyright © 2009, 2010, 2012, 2016 CCI. All rights reserved.

The contents of this document are confidential and proprietary to CCI. Unauthorized use, disclosure or reproduction is strictly prohibited.

## Analysis Plan

- o Female
- o Male
- Age (years):
  - o <65
  - o ≥65
- Geographic Region:
  - o North America (United States, Canada)
  - o Europe (Belgium, Czech Republic, France, Germany, Hungary, Estonia, Lithuania, Poland)
- Myasthenia Gravis Foundation of America (MGFA) classification at randomization
  - o Class I
  - o Class IIa
  - o Class IIb
  - o Class IIIa
  - o Class IIIb
  - o Class IVa

## 8. OUTPUT PRESENTATIONS

Appendix 1 shows conventions for presentation of data in outputs.

The templates provided with this SAP describe the presentations for this study and therefore the format and content of the summary tables, figures and listings to be provided by CCI.

## 9. DISPOSITION AND WITHDRAWALS

All subjects who provide informed consent will be accounted for in this study.

Subject disposition and reasons for discontinuation will be provided for the All Subjects Screened population. The list of protocol deviations (as defined in section 5.4), including inclusion and exclusion criteria, will be presented for the All Subjects Screened population.

## 10. DEMOGRAPHIC AND OTHER BASELINE CHARACTERISTICS

Demographic data and other baseline characteristics will be presented for the mITT population.

No statistical testing will be carried out for demographic or other baseline characteristics.

The following demographic and other baseline characteristics will be reported for this study:

- Age (years) - calculated relative to date of consent

Document: CCI

Author: PPD

Version Number:

Version Date:

Final 2.0  
12Apr2019

Template No: CCI

Effective Date: 01Apr2016

Reference: CCI

Copyright © 2009, 2010, 2012, 2016 CCI. All rights reserved.

The contents of this document are confidential and proprietary to CCI. Unauthorized use, disclosure or reproduction is strictly prohibited.

## Analysis Plan

- Sex
- Race
- Ethnicity
- Geographic Region
- Screening Weight (kg)
- Height (cm)
- Screening Body Mass Index (BMI) (kg/m^2)
- Baseline Total scores of QMG, MG composite, MG-QOL15, MG-ADL and Wells scores
- Baseline Fasting serum glucose, serum IgG trough, AChR antibodies, HbA1c
- Time since diagnosis (years) - calculated relative to date of consent
- Tests performed to confirm MG
- MGFA classification at time of diagnosis
- MGFA classification at screening
- MGFA classification at randomization
- MG treatment used during last six months
- Thymectomy history (yes/no)
- Baseline daily CS dose (prednisone equivalent) (mg, prescribed)
- Baseline daily CS dose (prednisone equivalent) level (15 – 40 mg, 41 – 60 mg)

**10.1. DERIVATIONS**

- $BMI (kg/m^2) = \text{weight (kg)} / \text{height (m)}^2$

**11. MEDICAL HISTORY**

Medical History information will be presented for the mITT population.

Document: CCI

Author: PPD

Version Number:

Version Date:

Final 2.0  
12Apr2019

Template No: CCI

Effective Date: 01Apr2016

Reference: CCI

Copyright © 2009, 2010, 2012, 2016 CCI. All rights reserved.

The contents of this document are confidential and proprietary to CCI. Unauthorized use, disclosure or reproduction is strictly prohibited.

## Analysis Plan

Medical History will be coded using Medical Dictionary for Regulatory Activities (MedDRA) version 17.1 and presented by System Organ Class (SOC) and Preferred Term (PT).

## 12. CONCOMITANT ILLNESSES

All Concomitant Illnesses will be reported as medical history or as adverse events, as appropriate, and will contribute to the corresponding summaries.

## 13. MEDICATIONS

Medications are reported on the Concomitant Medications page of the eCRF. They will be presented for the mITT population and coded using World Health Organization (WHO) Drug Dictionary Enhanced 01MAR2015. Medications will be summarized by Anatomical Therapeutic Chemical (ATC) Class Level 2 and Medication Sub-Class ATC Level 4. If the ATC Level 2 or 4 term is missing, the higher-level term will be used in the medication summary tables and data listing.

See Appendix 2 for handling of partial dates and times for medications. In the case where it is not possible to define a medication as prior or concomitant, the medication will be classified by the worst case; i.e. concomitant.

- 'Prior' medications are medications which started and stopped prior to the first dose of study medication.
- 'Concomitant' medications are medications which:
  - o started prior to, on or after the first dose of study medication;
  - o AND ended on or after the date and time of first dose of study medication or were ongoing at the end of the study.

The CS use will be analyzed as efficacy outcomes as described in Section 16. The prescribed and the actual use will also be presented in a listing.

## 14. STUDY MEDICATION EXPOSURE

Exposure to study medication in weeks will be presented for the Safety population.

The date of first study medication administration will be taken as the earliest start date of infusion from the eCRF Study Drug Infusion form. The date of last study medication will be taken as the latest stop date from the eCRF Study Drug Infusion form.

Interruptions, compliance, and dose changes are not taken into account for duration of exposure.

The total number of dosages, the total number of days of infusions, and the total volume infused (in mL) will be summarized on a per-subject basis. Note that subjects can have more than one infusion day per treatment visit. The initial loading dosage (2 g/kg) will be divided on 2 consecutive days with extension of up to 4 consecutive days to account for tolerability and/or weight >80 kg. The subsequent 12

Document: CCI

Author: PPD

Version Number:

Version Date:

Final 2.0  
12Apr2019

Template No: CCI

Effective Date: 01Apr2016

Reference: CCI

Copyright © 2009, 2010, 2012, 2016 CCI. All rights reserved.

The contents of this document are confidential and proprietary to CCI. Unauthorized use, disclosure or reproduction is strictly prohibited.

## Analysis Plan

maintenance dosages (1 g/kg) will be infused in one day with an extension to 2 consecutive days (divided dosages) to account for tolerability and/or weight >80 kg. For both loading and maintenance dosages the limit for blinded IGIV-C infusion is no more than 80 g/day, corresponding to an 80-kg body weight for a 1 g/kg per diem dosage.

In addition, the following variables will be derived and summarized separately for the loading dosage and the maintenance dosages:

On a per-subject basis:

- Number of dosage(s) received

On a per-dosage basis (one dosage/treatment visit may include multiple infusion days):

- Dosage in grams
- Dosage/body weight in g/kg
- Number of infusion days

On a per-infusion basis:

- Duration of infusion in hours

## 14.1. DERIVATIONS

Duration of exposure (weeks) = (date of last study medication administration – date of first study medication administration + 21)/7. The addition of 21 days is to take into account total exposure time to the study medication since the dosages are administrated every 3 weeks (Week 0, Week 3, Week 6, Week 9, Week 12, Week 15, Week 18, Week 21, Week 24, Week 27, Week 30, Week 33, and Week 36). Based on this derivation, the minimum exposure for any treated subject is 21 days, or 3 weeks.

In the below derivations, a dosage includes all infusion days within a given treatment visit.

Number of dosage(s) received will be determined directly from entries in the eCRF Study Drug Infusion form.

Dosage (g) = Total volume infused for the indicated dosage (mL) x Concentration of 0.1 (g/mL).

Dosage/body weight (g/kg) = Dosage (g) / Weight (kg), using the most recently available weight for the indicated treatment visit.

Number of infusion days will be determined directly from entries in the eCRF Study Drug Infusion form.

Duration of infusion in minutes will be calculated for each infusion day as: Stop time of infusion – Start time of infusion. Duration of infusion in hours will be calculated as: Duration of infusion in minutes / 60. If the time portion of either start or stop date/time is missing, then the duration will be missing for that infusion.

## 15. STUDY MEDICATION COMPLIANCE

Compliance to study medication, displayed as treatment compliance, infusion compliance, and overall

Document:	CCI	Version Number:	Final 2.0
Author:	PPD	Version Date:	12Apr2019

Template No:	CCI	Reference:	CCI
Effective Date:	01Apr2016		

Copyright © 2009, 2010, 2012, 2016 CCI. All rights reserved.  
The contents of this document are confidential and proprietary to CCI. Unauthorized use, disclosure or reproduction is strictly prohibited.

## Analysis Plan

compliance, will be presented for the Safety population.

## 15.1. DERIVATIONS

Treatment compliance will be calculated as the total volume infused divided by the total volume prepared, expressed as a percentage. The total volume prepared and dispensed by the pharmacist is the intended dose volume a subject should be given based on the body weight. This total volume prepared is recorded on the eCRF Study Drug Infusion form.

Infusion compliance will be calculated as the actual number of infusions received divided by the expected number of infusions, expressed as a percentage. Note that the number of days of infusions is a function of investigator choice based on both tolerability and weight. Subjects weighing > 80 kg will need to have infusions divided over more than 1 day as the limit for blinded study drug administration is 80 g/day. However, should a subject weigh more than 80 kg, the investigator may choose to divide the loading dose (2 g/kg) over 3 or 4 days as 3 or 4 daily infusions. For maintenance doses (1 g/kg) every 3 weeks, the choice is 1 or 2 days based on either tolerability or weight, given the mandatory dose limit of no more than 80 g/day. For the purpose of infusion compliance calculation, each loading or maintenance dose is counted as a single dosage. The expected number of dosages during the study is equal to 13 for subjects who complete the study. The total number of expected dosages for those who discontinue early is equal to the number of dosing visits, including completion of loading dose, up to the time of discontinuation. (For example, if a subject discontinues between weeks 6 and 9, the number of expected dosages is 3: one loading dose at Baseline, one maintenance dose at Week 3, and one maintenance dose at Week 6.)

Overall compliance will be calculated as treatment compliance multiplied by infusion compliance.

See calculations below.

- Treatment Compliance (%) to study medication will be calculated as follows:

$$\frac{[\text{Total Actual Volume Infused at 1st IP dose}] + \dots + [\text{Total Actual Volume Infused at last IP dose}]}{[\text{Total Volume Prepared for Infusion at 1st IP dose}] + \dots + [\text{Total Volume Prepared for Infusion at last IP dose}]} \times 100$$

- Infusion Compliance (%) to study medication will be calculated as follows:

$$\frac{[\text{Total Number of Dosages Received During the Study}]}{[\text{Total Number of Expected Dosages During the Study}]} \times 100$$

- Overall Compliance (%) to study medication will be calculated as follows:

$$(\text{Treatment Compliance} \times \text{Infusion Compliance}) / 100$$

Document: CCI

Author: PPD

Version Number:

Version Date:

Final 2.0  
12Apr2019

Template No: CCI

Effective Date: 01Apr2016

Reference: CCI

Copyright © 2009, 2010, 2012, 2016 CCI All rights reserved.

The contents of this document are confidential and proprietary to CCI. Unauthorized use, disclosure or reproduction is strictly prohibited.

